5.2 INDEX TESTS

The three index tests being evaluated are:

- 1) Vital signs at Day 0 (see Table 1)
- 2) Vital signs at Day 0 + lactate at Day 0
- 3) Vital signs at Day 0 and Day 1 + lactate at Day 0 and Day 1

The vital signs will indicate sepsis if one or more of the thresholds listed in Table 1 are exceeded. A lactate >2mmol/L will indicate sepsis. For tests combining vital signs and lactate, both will need to indicate sepsis to give a positive test result. For the test combining Day 0 and Day 1 measurements, a positive test will require the vital signs and lactate measurements to indicate sepsis at either Day 0 or Day 1.

Vital sign	Threshold
Respiratory Rate	>25 per minute
Heart rate	>120 beats per minute
Systolic Blood Pressure	< 90mmHg
Urine output	Less than 0.5ml/kg/hour
Mental state	Altered state

Table 1: Vital sign threshold values

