5.4 OUTCOME DEFINITIONS

The primary outcomes are the absolute differences in sensitivity and specificity between pairs of index tests: vital signs (Day 0) vs vital signs (Day 0) + lactate (Day 0), and vital signs (Day 0) + lactate (Day 0) vs vital signs (Day 0 and Day 1) + lactate (Day 0 and Day 1).

Secondary outcomes include:

- The absolute differences in sensitivity and specificity between vital signs (Day 0) alone and vital signs (Day 0) + lactate (Day 0) for maternal sepsis assessed at Day 0 only;
- The predictive value of vital signs (Day 0) alone compared to that of vital signs (Day 0) + lactate (Day 0) in those without sepsis at baseline, for maternal sepsis assessed at Day 1 only;
- The predictive value of vital signs (Day 0) alone compared to that of vital signs (Day 0) + lactate (Day 0) for the occurrence of severe morbidity and mortality from infection (WHO "severe maternal outcomes") (4), which is assessed daily until day 14 or discharge or death, if sooner;
- The sensitivity and specificity of vital signs (Day 0) + lactate (Day 0) and vital signs (Day 0 and Day 1) + lactate (Day 0 and Day 1) by: pregnancy status (pregnant or postdelivery/post miscarriage/post-abortion), source of sepsis (genital tract or nongenital tract) and condition on admission (stable or critical);
- The sensitivity and specificity of the primary index test comparisons including those women discharged early, assuming that they did not have sepsis;
- In an exploratory analysis, the sensitivity and specificity of each index test will be estimated based on different threshold values for lactate;
- To explore the use of an alternative reference standard, in which the SOFA score is modified to use maternity specific ranges for creatinine and platelet concentration, an independent expert review group will examine all cases with discordant results to adjudicate based on clinical features, clinical management, response to treatment and outcomes, if the case fitted the WHO definition of maternal sepsis. The pattern of discrepant results will be investigated descriptively.
 - 5.5 SAMPLE SIZE

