7.3 FINAL ANALYSIS

Primary analysis

We will estimate the sensitivity, specificity, positive predictive value (PPV) and negative predictive value (NPV) of the three index tests to detect sepsis assessed at Day 0 and Day 1. The 95% CIs for the estimates will be calculated using the Wilson method for proportions. To compare the accuracy of sepsis diagnosis by vital signs alone versus vital signs + lactate, we will fit separate generalized estimating equation (GEE) models for women with and without sepsis to estimate absolute differences in sensitivity and specificity, respectively. This approach exploits the paired nature of the data. We will compute absolute differences

in sensitivities and specificities from the GEE models using a post-estimation procedure with Cls computed using the delta method.

Secondary analyses

We will assess (a) index tests based on Day 0 only against Day 0 reference standard to determine immediate diagnostic value; (b) index tests based on Day 0 only against Day 1 reference standard in those without sepsis at baseline to determine short-term predictive value; and (c) index tests based on Day 0 only with occurrence of infection related "severe maternal outcome" (near miss or maternal mortality) (4) prior to hospital discharge to determine predictive value for severe morbidity or mortality (5) assuming that those women discharged prior to the Day 1 assessment did not have sepsis. Sensitivity, specificity, PPV, and NPV will be calculated for each test. In addition, for each of the analyses above, we will estimate absolute differences in sensitivity and specificity of vital signs alone versus vital signs (Day 0) + lactate (Day 0).

Pre-specified subgroup analyses will include pregnancy status (pregnant or postnatal) and illness severity to explore if the test accuracy of lactate in addition to vital signs alone varies by these subgroups.

Exploratory receiver operating characteristic (ROC) curve analyses will examine the effect of adjusting the threshold value for lactate on the sensitivity and specificity of the index tests.

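### The two prediction outcomes in 5.4 are worded as comparisons of predictive value, but 7.3 contrasts only sensitivity and specificity, whose direction the AND rule fixes in advance

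*SAP*

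**What the plan says.** SAP 5.4 lists three secondary outcomes that compare vital signs at Day 0 with vital signs plus lactate at Day 0.

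- For sepsis at Day 0 it names the measure: "The absolute differences in sensitivity and specificity between vital signs (Day 0) alone and vital signs (Day 0) + lactate (Day 0").
- For Day 1 sepsis in women without sepsis at baseline, and for severe maternal outcome, the wording changes to "The predictive value of vital signs (Day 0) alone compared to that of vital signs (Day 0) + lactate (Day 0").

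In SAP 7.3 these are secondary analyses (a), (b) and (c). For single tests it says: "Sensitivity, specificity, PPV, and NPV will be calculated for each test". For the comparison between tests it says: "we will estimate absolute differences in sensitivity and specificity of vital signs alone versus vital signs (Day 0) + lactate (Day 0"). No difference, ratio, paired interval or test for PPV or NPV appears anywhere in the document.

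The only paired model described, under the primary analysis, is "separate generalized estimating equation (GEE) models for women with and without sepsis to estimate absolute differences in sensitivity and specificity, respectively". Under the combination rule in 5.2, "both will need to indicate sepsis to give a positive test result".

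**The concern.** Two declared secondary outcomes read as comparisons of predictive value, and no analysis in 7.3 makes that comparison. The contrasts that 7.3 does make have a direction set by the construction of the combined test. A reader who sees lower sensitivity and higher specificity learns that the positivity rule became stricter, which was known beforehand.

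The objective for severe outcomes asks whether lactate improves prediction. For a clinician, that means whether a woman positive on both components is at higher risk than a woman positive on vital signs. The PPV difference answers this, and nesting does not fix its sign. If it is not planned, either the PPVs will be compared informally from separate estimates or a method will be chosen after the data are seen.

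**Working it through.** **Inputs from the SAP.** Prevalence 40%, total 346, baseline sensitivity 30–60%, 75% as an illustrative specificity, 500 recruited (5.5); AND rule (5.2); two-sided 5% (6.1).

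**Assumptions not in the SAP.** Vital-sign sensitivity 50% (within the stated range) and specificity 75%; lactate performance among vital-sign positives; event counts of 50 in 500 for (c) and 24 in 232 for (b). The case of 138 in 346 is the primary-analysis planning size and serves as an upper case.

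**The plan's own figure.** The SAP gives no figure for a PPV or NPV comparison. Its 346 is for sensitivity, and it nearly reproduces. With a 20-point gain from 40% to 60% and the tests independent given disease, the discordant share is 0.4×0.4 + 0.6×0.6 = 0.52. Then n = [1.96√0.52 + 1.2816√(0.52 − 0.04)]²/0.04 = 132.4. Adding the continuity term 1/0.20 = 5 gives 137.4, so 138 women with sepsis, and 138/0.40 = 345.

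**Step 1: what the planned contrasts show when lactate is worthless.** Take 138 women with and 208 without the outcome, and a lactate positive in half of each group.

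- Sensitivity: 50% → 25%. Specificity: 75% → 87.5%.
- PPV: 69/121 = 57.0% → 34.5/60.5 = 57.0%, unchanged.
- NPV: 156/225 = 69.3% → 182/285.5 = 63.7%, a fall.

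Both planned contrasts move by a wide margin although lactate adds nothing. The PPV difference is zero. The NPV difference is not, so NPV does not isolate added information.

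**Step 2: why the planned model does not help.** The GEE models are fitted within reference-standard groups, so they estimate the probability of a positive test given status. PPV and NPV condition the other way.

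**Step 3: one worked case.** Same sizes, with lactate 60% sensitive and 70% specific among vital-sign positives. Positives on vital signs: 69 + 52 = 121. Positives on both: 41 + 16 = 57.

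- PPV, vital signs: 69/121 = 57.0% (Wilson 48.1–65.5%).
- PPV, combined: 41/57 = 71.9% (Wilson 59.2–81.9%). The intervals overlap.
- Because the tests are nested, the PPVs are equal exactly when risk is the same in lactate-positive and lactate-negative women among vital-sign positives: 41/57 against 28/64.
- Score test: z = (0.719 − 0.4375)/√[0.570×0.430×(1/57 + 1/64)] = 3.13, chi-square 9.77, p = 0.0018.
- Paired difference: (64/121)×(0.719 − 0.4375) = 14.9 points. Holding 64/121 fixed, SE = 0.529×√(0.719×0.281/57 + 0.4375×0.5625/64) = 4.5 points, so a 95% CI of about 6 to 24 points.

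**Step 4: how often this happens.** Simulation, 20,000 replicates per row, vital signs 50/75:

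| Events / women | Lactate sens/spec | Paired PPV test detects | Wilson intervals separate |
|---|---|---|---|
| 138/346 | 60/70 | 91% | 13% |
| 50/500 | 60/70 | 80% | 7% |
| 24/232 | 60/70 | 50% | 1% |
| 138/346 | 80/80 | 100% | 97% |
| 50/500 | 80/80 | 100% | 96% |
| 24/232 | 80/80 | 98% | 39% |

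With an uninformative lactate (50/50) the paired test rejects in about 5% at all three sizes, which is its correct level.

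A second grid took 300 or 500 women, events in 10–20%, vital-sign sensitivity 50–60% and lactate 60/60 to 80/70. PPV gains of about 7–14 points gave paired power of 30–96% against interval separation in 0–10%. Gains of about 16–24 points gave 82–100% against 5–92%.

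**The case against.** **The term may not mean PPV and NPV.** Section 7.3 describes analysis (b) as done "to determine short-term predictive value", in parallel with a diagnostic value for (a), and it writes PPV and NPV in full where it means the statistics. On that reading the sensitivity and specificity differences are the intended comparison. This stands as an ambiguity. The change of wording directly after the Day 0 bullet makes PPV and NPV the more natural reading, and 5.4 needs an edit on either one.

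**A reader might infer that the SAP will judge PPVs by whether separate intervals overlap.** It does not say so. The sentence "The 95% CIs for the estimates will be calculated using the Wilson method for proportions" stands under the primary analysis, and the secondary paragraph only says that PPV and NPV will be calculated. Non-overlap is also a conservative criterion in any setting, so the last column of the table shows what separate estimates can fail to reveal, not the power of a planned test.

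**A reader might infer that real gains would usually be hidden.** The figures do not support this in general. With a strong lactate the intervals mostly separate at the two larger sizes. The loss concerns modest gains and few events.

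**The information is in the data.** The combined PPV is higher exactly when the ratio of sensitivities exceeds the ratio of false-positive rates; in the worked case 41/69 = 0.59 against 16/52 = 0.31. This is true of the point estimate. What is missing is a valid interval for the comparison, and two separate differences do not give one.

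**These are secondary analyses, and (c) is exploratory.** This is also true. It limits the weight of the point but does not remove the mismatch.

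**Conclusion.** The point holds in a limited form. Sections 5.4 and 7.3 do not join up for analyses (b) and (c): the outcome is worded as a comparison of predictive value, and the only specified contrasts are in sensitivity and specificity. Under the AND rule the direction of those contrasts is known before any data are collected, so alone they cannot show whether lactate improves prediction. The models fitted by sepsis status cannot supply the missing contrast.

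The practical size depends on event rates and lactate performance that the SAP does not give. For a modest lactate (60/70) a paired comparison detects the PPV gain in 50–91% of studies, while separate intervals part in 1–13%. For a strong one (80/80) they part in 39–97%. The primary analysis is unaffected. The change should be made before analysis, because it also closes off a later choice of measure.

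**What to change.** In 5.4, state for the Day 1 sepsis and severe-maternal-outcome bullets that PPV and NPV are the measures meant.

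In 7.3, for (b) and (c), add the absolute differences in PPV and in NPV between vital signs and vital signs plus lactate at Day 0, each with a paired 95% CI. Name one method: a bootstrap over women, the weighted generalised score method, or a GEE with reference status as the outcome among test-positive (or test-negative) records, clustered on woman. Keep the sensitivity and specificity differences alongside.

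Add a sentence on interpretation: under the AND rule NPV tends to fall even when lactate is uninformative, so the PPV difference is the one that reflects added information.

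The cost is SAP wording and minor programming on data already collected. The downside is two more secondary contrasts per analysis, in a plan that makes no adjustment for multiple testing.

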3 OBJECTIVES

The primary objective is to evaluate the diagnostic accuracy of maternal venous lactate measurement in addition to maternal vital signs (at Day 0 and/or Day 1), in maternal sepsis in low-resource health facility settings in Malawi, Uganda and Pakistan.

Secondary objectives are to:

• evaluate the immediate diagnostic value of lactate testing at Day 0 in addition to maternal vital signs in maternal sepsis at Day 0 (reference standard at Day 0 only);

- assess the short-term predictive value of lactate testing at baseline, in addition to vital signs, for maternal sepsis at 24-hours (24-hour reference standard) in those without sepsis at baseline;
- explore if baseline venous lactate, in addition to vital signs, improves prediction of severe morbidity and mortality from infection;
- explore if the diagnostic accuracy of lactate in addition to maternal vital signs alone, varies by the pre-specified subgroups of pregnancy status (pregnant or post-delivery / post miscarriage / post-abortion), source of sepsis (genital tract or non-genital tract) and condition on admission (stable or critical);
- examine the effect of adjusting the threshold values for lactate assessment on the sensitivity and specificity of the index tests;
- explore the use of an alternative reference standard in which the Sequential Organ Failure Assessment (SOFA) score is modified to use maternity specific ranges for creatinine and platelet concentration.

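### The subgroup outcome omits vital signs alone, so it does not give lactate's added value by subgroup, and sections 3, 5.4 and 7.3 do not list the same subgroups

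*SAP*

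**What the plan says.** The objective in SAP section 3 is to "explore if the diagnostic accuracy of lactate in addition to maternal vital signs alone, varies by the pre-specified subgroups of pregnancy status", followed by the other two subgroups, "source of sepsis (genital tract or non-genital tract) and condition on admission (stable or critical".

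Section 5.4 turns this into an outcome. It begins "The sensitivity and specificity of vital signs (Day 0) + lactate (Day 0) and vital signs (Day 0 and Day 1", goes on to lactate at both days, and keeps all three subgroups, including "source of sepsis (genital tract or nongenital tract) and condition on admission (stable or critical". It names the two index tests that contain lactate. Vital signs alone, the first index test in section 5.2, are not in the item, and neither is a difference between tests.

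The other comparative outcomes in section 5.4 are built differently. "The primary outcomes are the absolute differences in sensitivity and specificity between pairs of index tests", and the first of those pairs has vital signs alone as comparator. The first three secondary outcomes also set vital signs alone against vital signs plus lactate.

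Section 7.3 says: "Pre-specified subgroup analyses will include pregnancy status (pregnant or postnatal) and illness severity to explore if the test accuracy of lactate". The rest of that sentence gives the same added-value aim as section 3. It names two subgroups and gives no estimand or model for them. Its sentence on between-test differences reads "for each of the analyses above, we will estimate absolute differences in sensitivity and specificity of vital signs alone". That sentence closes the paragraph on secondary analyses (a) to (c), and the subgroup paragraph comes after it.

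**The concern.** The objective is about an increment: what lactate changes relative to vital signs alone, and whether that change differs between subgroups. An outcome that reports only the combined tests measures something else. The accuracy of vital signs may itself differ between, say, stable and critical women. A gap between subgroups in the combined test could then come from the vital signs, and equal results could hide a real difference in what lactate does.

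The second issue is which subgroups were pre-specified. Section 7.3 uses that term for a list that is shorter than, and labelled differently from, the list in sections 3 and 5.4. If this is not settled before analysis, the final report can be faulted whichever list it follows.

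**Working it through.** **Step 1: the sections side by side.**

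| | Section 3 | Section 5.4 | Section 7.3 |
|---|---|---|---|
| Question | Added value of lactate by subgroup | Accuracy of two lactate-containing tests by subgroup | Added value of lactate by subgroup |
| Vital signs alone by subgroup | Implied as comparator | Not listed | Implied by the aim, not specified |
| Between-test difference by subgroup | – | Not defined | Not defined; the sentence on differences covers (a) to (c) |
| Pregnancy status | Yes; non-pregnant level covers delivery, miscarriage and abortion | Same | Yes; non-pregnant level called *postnatal* |
| Source of sepsis | Yes | Yes | Not named |
| Condition on admission | Yes, stable or critical | Same | *Illness severity*, levels not given |

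**Step 2: what the listed outcome identifies.** Section 5.2 requires both vital signs and lactate to be positive. At Day 0, every woman positive on test 2 (vital signs plus lactate) is therefore positive on test 1 (vital signs alone). Hence:

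- Se2 ≤ Se1 ≤ 1, so the change Se2 − Se1 lies between Se2 − 1 and 0.
- Sp1 ≤ Sp2, so the change Sp2 − Sp1 lies between 0 and Sp2.

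Knowing test 2 alone gives these bounds and no more. For Se2 = 40%, the change in sensitivity can be anything from −60 to 0 points. Test 3 does not narrow this: it adds Day 1 measurements and also contains lactate, so comparing tests 2 and 3 addresses repetition, not the addition of lactate.

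**Step 3: two illustrations.** All sensitivities are assumed; the SAP gives none by subgroup.

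| | Subgroup | Vital signs alone | Test 2 (in the listed outcome) | Change |
|---|---|---|---|---|
| Hidden difference | A | 45% | 40% | 40 − 45 = −5 |
| | B | 70% | 40% | 40 − 70 = −30 |
| Same change, visible gap | A | 60% | 40% | 40 − 60 = −20 |
| | B | 80% | 60% | 60 − 80 = −20 |

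In the first case the listed outcome shows no subgroup difference, although the changes differ by 25 points. In the second it shows a 20-point gap, although the absolute change is the same.

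**Step 4: why vital signs alone must be shown beside the difference.** Let f be the share of vital-sign-positive septic women who are also lactate-positive. Then Se2 = f × Se1, and the change is −(1 − f) × Se1, which depends on Se1 even when f is constant. In the second illustration the absolute changes are equal, but f is 40/60 = 67% and 60/80 = 75%. The reader needs both quantities.

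**Step 5: precision of the proposed contrast.** The SAP gives no figure for subgroups, so there is none to reproduce. Its total of 346 concerns the whole cohort. An unpaired two-proportion formula with continuity correction at 40% versus 60% gives 140 cases, and 140/0.40 = 350, close to it. I use the SAP's totals only to count septic women at its 40% prevalence: 0.40 × 346 ≈ 138 and 0.40 × 500 = 200.

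Under the rule in section 5.2, all discordance at Day 0 runs one way, so the discordant proportion equals the size of the drop, |d|. The variance per woman is v = |d| − d², and the 95% half-width of the between-subgroup contrast is 1.96 × √(v/n₁ + v/n₂). I assume the same v in both levels.

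- |d| = 0.10 (v = 0.09), 200 women split 50/50: 1.96 × √(0.09/100 + 0.09/100) = 0.083.
- |d| = 0.20 (v = 0.16), 138 women split 50/50: 1.96 × √(0.16/69 + 0.16/69) = 0.133.
- |d| = 0.10, 200 women split 25/75: 1.96 × √(0.09/50 + 0.09/150) = 0.096.
- |d| = 0.20, 138 women split 25/75: 1.96 × √(0.16/34.5 + 0.16/103.5) = 0.154.

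The range is about 8 to 15 points. The largest possible v is 0.25 (at |d| = 0.5); with 138 women split 25/75 it gives 1.96 × √(0.25/34.5 + 0.25/103.5) = 0.193.

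**The case against.** The strongest reply is that section 7.3, which governs the analysis, states the right aim. Vital signs at Day 0 are an index test in their own right, Appendix 1 schedules them for every woman, and the primary analysis already defines a paired GEE difference that could be run within subgroups. A reader might infer from section 5.4 that the trial cannot show whether lactate's added value varies. The document does not support that: the data allow the analysis. What stands is that no section specifies it, and that the outcome which is specified measures something else.

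On the lists, section 7.3 says its analyses *will include* two subgroups, which is not strictly a closed list, and sections 3 and 5.4 agree on three. The intent is therefore fairly clear. The disagreement in names and number still needs removing.

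A reader might also infer that specificity by source of sepsis cannot be estimated, because women without sepsis have no such source. The SAP nowhere defines the variable only for septic women. Inclusion criterion 2 requires suspected or confirmed infection of every participant, and section 5.4 plans specificity by source. The label is loose; the analysis is not ruled out.

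Finally, the objective is exploratory and no subgroup power is claimed, so within-subgroup paired differences with intervals might be thought enough. That is fair as regards formal testing. But the question is whether the increment varies, and a contrast with its interval answers that more directly than two separate intervals.

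**Conclusion.** The point holds as a mismatch between objective and outcome. As written, section 5.4 does not deliver the increment due to lactate within any subgroup, and section 7.3 does not supply it. The size of what could be missed is illustrative only: identical listed results can go with changes of −5 and −30 points under the assumed sensitivities. The bounds in step 2 rest only on the both-positive rule in section 5.2. Separately, the subgroup list falls from three to two in section 7.3, with changed labels.

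This affects an exploratory secondary objective and leaves the primary result untouched. It should be corrected because a stated objective would otherwise not be answered by its own outcome, and the correction is cheap.

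**What to change.** 1. In sections 5.4 and 7.3, define the subgroup outcome as the paired absolute differences in sensitivity and specificity, vital signs at Day 0 versus vital signs plus lactate at Day 0, within each level of each subgroup, with 95% CIs.
2. Take these from the planned GEE models for women with and without sepsis, adding a test-by-subgroup term. Report the between-subgroup contrast on the absolute scale, using the post-estimation step and delta method already planned. Label it exploratory.
3. Report sensitivity and specificity of vital signs alone by subgroup next to the differences, for the reason in step 4 of the working.
4. Use one list and one set of labels in sections 3, 5.4 and 7.3: pregnancy status, with post-miscarriage and post-abortion women explicitly placed; source; and condition on admission with its two levels. Label source as the source of suspected or confirmed infection, so that it clearly applies to all women.

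The cost is SAP wording and one added term per subgroup model; no further test data are needed. The downside is wide intervals for the contrasts, which the report should state plainly.

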We aim to recruit 500 women to the study in total. In computing sample sizes, we estimated that an increase of 20% in sensitivity would be both feasible and clinically important. This equates to detecting an additional sepsis case for every 5 women who have sepsis. Assuming a prevalence of 40%, defining statistical significance at the 5% level and ensuring 90% power, up to 346 participants in total would ensure we are appropriately powered across a range of baseline sensitivities between 30 and 60% when vital signs alone are used. It is important to also estimate specificity to detect any important increase in false positives. With 200 patients without sepsis, the specificity of each test will be estimated with 95% confidence interval (CI) width of 15 percentage points for a specificity of 75% and width less than 10 percentage points for a specificity of 90%. This is adequate precision to allow important changes to be estimated. Allowing for loss to follow-up and missing / laboratory results, we consider an initial sample size of 500 as appropriate to allow the study to have adequate power to test these hypotheses. This number of cases will be feasible to collect within 12 months, based on current infection rate data from all sites.

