6 STATISTICAL PRINCIPLES

6.1 LEVELS OF CONFIDENCE AND P-VALUES

All confidence intervals presented will be 95% and two-sided. All applicable statistical tests will be two-sided, with a p-value of ≤ 0.05 considered to be statistically significant.

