7.2 INTERIM ANALYSIS

Interim analyses will be conducted at 6 months during the trial recruitment. The analyses will include a description of key demographic and clinical characteristics of women with and without maternal sepsis and the estimate of prevalence of sepsis. Based on the estimated prevalence, the sample size requirements will be revisited to assess whether the target sample size needs to be adjusted. The completeness of variables used for the index and reference tests will be assessed, along with the quality of the data collection. The number and characteristics of the women missing a Day 1 assessment will also be assessed. The TOC Subgroup will consider these results, accruals, as well as any data from external trials to make an ongoing judgement on recommendations to be made according to their terms of reference.

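### SAP 5.5's 90% power with up to 346 women does not describe the nested, paired comparisons of 5.2 and 7.3; the mismatch is conservative, but the gain powered for cannot occur in the first primary pair

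*SAP*

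**What the plan says.** Section 5.5 sets the effect size: "we estimated that an increase of 20% in sensitivity would be both feasible and clinically important". It makes clear that the effect is absolute: "This equates to detecting an additional sepsis case for every 5 women who have sepsis". With an assumed prevalence of 40%, and "defining statistical significance at the 5% level and ensuring 90% power", it concludes that "up to 346 participants in total would ensure we are appropriately powered across a range of baseline sensitivities between 30 and 60" (per cent; the baseline here is the vital-signs test without lactate). Section 5.5 separately asks for 200 women without sepsis for the precision of specificity, in order to pick up a rise in false positives, and sets the target at 500 after losses. Section 6.1 adds: "All applicable statistical tests will be two-sided".

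Section 5.2 defines the tests. Vital signs plus lactate is positive only if both components are positive. For the two-day test, "a positive test will require the vital signs and lactate measurements to indicate sepsis at either Day 0 or Day 1".

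Section 5.4 names two primary pairs: vital signs v vital signs + lactate, both at Day 0; and the Day 0 combination v the Day 0/Day 1 combination. Section 7.3 fits GEE models to each comparison and notes: "This approach exploits the paired nature of the data".

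Section 7.2 plans a review at 6 months: "Based on the estimated prevalence, the sample size requirements will be revisited to assess whether the target sample size needs to be adjusted".

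**The concern.** Section 5.2 makes each primary pair nested. Every woman positive on vital signs + lactate (Day 0) is also positive on vital signs (Day 0), and every woman positive on the Day 0 combination is also positive on the Day 0/Day 1 combination. For nested tests the discordant women all lie in one direction, so the discordant proportion equals the difference in sensitivity whatever the baseline. A requirement that varies with baseline sensitivity, as in 5.5, suggests that nesting was not used.

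Three things are at stake:

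- the 90% figure is not the power of the written comparisons;
- the direction powered for, a gain over vital signs alone, is impossible for the first pair;
- the same figure may feed the interim review of sample size.

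**Working it through.** **Inputs.** From the SAP: two-sided 5% (5.5, 6.1), so z = 1.960; 90% power, z = 1.2816; difference 0.20; prevalence 0.40; baseline 0.30 to 0.60 (5.5); combination rules (5.2). The SAP gives no formula and no discordance. Two assumptions are compared: independence of the two tests given sepsis, and full nesting.

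**1. The plan's figure in cases.** 346 × 0.40 = 138.4 women with sepsis.

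**2. Reproducing it.** Within the 30 to 60% range the worst case is 40% v 60%.

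- Two-sample formula: (1.960√(2·0.5·0.5) + 1.2816√(0.24 + 0.24))² / 0.04 = 129.3 cases; /0.40 = 323 women. With continuity correction: 139.1 cases, 348 women.
- McNemar under independence: discordance 0.4·0.4 + 0.6·0.6 = 0.52. (1.960√0.52 + 1.2816√0.48)² / 0.04 = 132.4 cases, 331 women. The simpler form (1.960 + 1.2816)²·0.52/0.04 gives 136.6 cases, about 342 women.
- Exact McNemar under independence with 138 cases: power 0.896.

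So 346 lies in this region, although no variant gives it exactly. The two-sample requirement moves with baseline (124, 129, 124 and 108 cases at 30, 40, 50 and 60%), as 5.5's wording implies.

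**3. The written design.** Discordance = difference = 0.20, at any baseline.

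- McNemar formula: (1.960√0.20 + 1.2816√0.16)² / 0.04 = (0.8765 + 0.5126)² / 0.04 = 48.2 cases; /0.40 = about 121 women.
- Exact McNemar: at least 6 discordant women are needed (2·0.5⁶ = 0.031; 2·0.5⁵ = 0.0625). With discordants ~ Binomial(n, 0.20), n = 45 gives power 0.910; 45/0.40 = 113 women.
- Across the asymptotic variants tried: 33 to 53 cases, 83 to 133 women.

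**4. Power with 138 cases, nested, exact McNemar.** For 20 points: 1 − P(discordants ≤ 5) > 0.999. For 7 points: 0.926.

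**5. Direction.** If vital signs + lactate is positive only when vital signs are positive, its sensitivity cannot exceed that of vital signs and its false positives cannot be more numerous. For the first pair, step 3 therefore describes a 20-point fall. Only the Day 0/Day 1 test can gain, and its comparator is the Day 0 combination, not the vital signs alone to which the 30 to 60% range refers.

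**6. Interim, if the basis were reused.** Women needed before losses:

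| Prevalence | 138.4 cases | 48.2 cases | 200 without sepsis |
|---|---|---|---|
| 40% | 346 | 121 | 333 |
| 25% | 554 | 193 | 267 |
| 20% | 692 | 241 | 250 |
| 15% | 923 | 322 | 235 |

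The 346 basis exceeds 500 below 138.4/500 = 27.7% prevalence; the nested basis does so only below 48.2/500 = 9.6%.

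**The case against.** The strongest reply is that 5.5 gives a ceiling. If true power exceeds 99.9%, then up to 346 women still ensure 90%, so the figure is safe. That stands: the trial is not underpowered. It also stands that the independence assumption is inferred, because the SAP names no method and no variant returns exactly 346.

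A reader might infer that the study needs only about 120 women. The documents do not support that. The requirement of 200 women without sepsis alone needs 200/0.60 = 333 at 40% prevalence. With 48 cases, the 95% half-width for a 20-point nested difference would be 1.96√(0.16/48) = 11 points, against 6.7 with 138.

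A reader might also infer that the interim review will wrongly enlarge the trial. Section 7.2 does not say so. It states no formula or rule, does not mention 346, and leaves the recommendation to the oversight subgroup's judgement. The risk arises only if prevalence is about 10 to 28% and the 5.5 calculation is reused. In that range the specificity requirement would not itself call for more than 500, so the sensitivity figure would drive any increase.

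Finally, 7.3 specifies GEE with delta-method intervals, not McNemar. The replacement numbers are therefore indicative and must themselves be matched to the planned analysis.

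**Conclusion.** The point holds in a limited form. The 90% power in 5.5 does not describe the comparisons defined in 5.2 and analysed in 7.3. For a 20-point difference, the nested requirement is about 48 sepsis cases against about 138, nearly a threefold excess, and it does not depend on baseline sensitivity. This rests on the both-positive and either-day rules as written and on the McNemar formula. An either-positive rule for lactate would also nest the first pair, with the same count but the opposite direction.

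The numerical mismatch is conservative and gives no reason to change the target of 500. The more substantive defect is direction: the gain in sensitivity over vital signs alone, and the rise in false positives that 5.5 guards against, cannot occur for the first primary pair at any sample size. The interim consequence is a conditional risk, not something the plan prescribes.

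**What to change.** - Reconcile 5.2 with 5.5, so that the combination rule and the hypothesised effect agree.
- For each primary pair, state in 5.5 the direction of the effect, the correct comparator, the assumed discordance, and a paired calculation matched to the GEE analysis, with power or the CI width for the difference restated. A single sentence on power that gives no direction would hide the contradiction for the first pair.
- In 7.2, compare the number of sepsis cases with complete index and reference data with that requirement, together with the 200 women without sepsis, rather than rescaling 346 by prevalence.
- Keep the target of 500.

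The cost is SAP wording only, with no extra participants. The downside is that the case for 500 then rests on precision and missing data rather than on 90% power for 20 points.
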